4.2 Blinding

Subjects, site personnel, the Data and Safety Monitoring Board (DSMB), EAC, and the Medical Monitor are initially blinded to the randomization assignment. Blinding will be maintained through the data cutoff for the primary efficacy analysis after which the blind will be lifted for the DSMB. The DSMB may be unblinded to individual assignments earlier as needed to adjudicate certain adverse events. Individual randomization assignments will not be revealed to

the subjects, site personnel, EAC or the Medical Monitor until the study is completed. Sites will be provided an emergency unblinding code if it becomes medically necessary to know the treatment group assigned for a particular subject.

Subjects will be randomized to receive either RBX2660 or placebo through an Interactive Response Technology (IRT) System prior to receiving the first assigned blinded study treatment. Randomization assignment is revealed to Rebiotix Operations Department personnel for product preparation and shipment. The Rebiotix Kit is shipped to the site in a sealed carton that is only opened by the IP administrator at the time of administration, out of view of the subject and other site personnel. While the IP administrator will not have access to the actual randomization assignment, it may be possible to guess through visualization at the time of enema preparation and administration. Additionally, subjects will be instructed to disregard any product characteristics that may become evident during or after administration such as the presence or absence of color or odor. To limit study bias, the IP administrator is not allowed to perform any of the subject study assessments.

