4.4 Determination of Sample Size

To demonstrate a 69% success with one dose of the RBX2660 treatment group vs. 47% success in the Placebo control group, 240 subjects are required (power > 90%, nominal 2.5% type I error rate). Up to an additional 30 subjects will be enrolled to allow for a 10% loss-to-follow up rate, for a total of approximately 270 subjects. Considering the 2:1 randomization, this results in approximately 180 subjects in the RBX2660 arm and 90 subjects in the Placebo arm. Enrolled subjects who have signed consent and withdraw for any reason prior to administration of the first blinded enema will be replaced without counting toward the sample size cap. Replacement subjects will be randomized to ensure proper blinding.

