6.3.1 Intent-to-Treat Population

Analysis of the primary efficacy endpoint will be done using the Intent-to-Treat (ITT) population as a sensitivity analysis. The ITT population is defined as all randomized subjects. Subjects will be analyzed according to the randomized treatment rather than the actual treatment received regardless of treatment misallocations. Re-randomized subjects will be summarized using their second treatment assignment (see Section 4.3 for details). Randomized subjects who exited prior

to receiving blinded treatment will not be included in the analysis. Randomized subjects in whom blinded treatment was attempted but delivery of the enema was not successful will be counted as treatment failures. Randomized and treated subjects who exited prior to their 8-week efficacy assessment will be counted as treatment failures even if protocol required treatment failure documentation is not on file. Additionally, the secondary efficacy endpoints may be evaluated using the ITT population.

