6.3.2 Modified Intent-to-Treat Population

For the Modified Intent-to-Treat (mITT) population, subjects will be analyzed according to the randomized treatment assignment despite any treatment misallocations.

Additionally, the mITT population will be defined as all randomized subjects who successfully received blinded treatment but excluding;

- subjects who withdrew prior to treatment;
- subjects in whom treatment was attempted but not completed and;
- subjects who discontinue from the study prior to evaluation of treatment failure/success for the primary endpoint if the reason for exit is not related to CDI symptoms. Reason for exit will be captured on the exit form to allow for identification of such subjects.

Examples of reasons unrelated to CDI symptoms may include;

- Withdrawal of consent
- Death unrelated to CDI

Subjects who were exited prior to the 8-week efficacy assessment due to CDI related symptoms will be counted as treatment failures even if documentation as required per the protocol is not on file for the treatment failure.

The mITT population will be used for the primary efficacy reporting purposes. The mITT population will also be used for secondary and exploratory endpoints evaluation. The analysis of the ITT and PP populations may also be provided in addition to the mITT for purposes of regulatory evaluation.

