7.6.1.2 Sensitivity Analysis for the Primary Efficacy Endpoint

The primary efficacy analysis will be repeated using the ITT and PP population to assess the sensitivity of the primary endpoint regardless of the outcome of the mITT primary efficacy analysis. The ITT analysis will serve as the conservative analysis as it considers all subjects who exit prior to the 8-week efficacy assessment as treatment failures regardless of treatment failure documentation.

Three groups of sensitivity analyses will be performed to assess the sensitivity of the results to the borrowing of historical data from the previous Phase 2B study (Protocol 2014-01) of RBX2660.

- 1) A Pearson's chi-square test will be used to test the null hypothesis that the response rate in the treatment group is equal to that of the control group. In addition, two-sided 95% confidence intervals for the difference in response rate between arms will be calculated using a normal distribution approximation. This sensitivity analysis will be conducted using the mITT, ITT, and PP populations using data from the 2017-01 study only.
- 2) Sensitivity of the primary analysis (Bayesian analysis) to the analysis population (ITT, PP) using Bayesian analysis.
- 3) Sensitivity of the primary analysis (Bayesian analysis) to the following different sensitivity analysis populations from the 2014-01 study using Bayesian analysis. The **2014-01 Sensitivity Analysis Population #1** represents the ITT population from the 2014-01 study, and the **2014-01 Sensitivity Analysis Population #2** represents the

population used for the primary analysis inclusive of one subject in Group C who was exposed to product but did not receive the full enema.

2014-01 Sensitivity Analysis Population #1				2014-01 Sensitivity Analysis Population #2			
2014-01 Treatment Group	# Subjects	# Responders	Response Rate	2014-01 Treatment Group	# Subjects	# Responders	Response Rate
A	45	25	0.556	A	41	25	0.610
B	44	19	0.432	B	44	19	0.432
C	44	25	0.568	C	43	25	0.581

Efficacy analysis will be repeated without the borrowing of historical data from the Phase 2B study (Protocol 2014-01) using the mITT, ITT, and PP populations.

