7.6.2 Analysis Secondary Efficacy Endpoint

A hierarchical, closed-testing procedure will be utilized for the secondary endpoint: If the null hypothesis for the primary efficacy endpoint is rejected, the secondary endpoint will be analyzed. The secondary endpoint will be tested at a two-sided 0.05 significance level.

7.6.2.1 Sustained clinical response of RBX2660 vs. Placebo.

The null hypothesis of interest is that the rates of sustained clinical response (i.e., the rate of CDI occurrence with treatment success of the presenting CDI recurrence and no new CDI episodes for greater than 8 weeks after completing a blinded study treatment) are the same between the RBX2660 group and the Placebo group during the 6 months of follow-up. The alternative is that there is a difference in sustained clinical response rates. A Pearson's chi-square test will be used to test the null hypothesis that the response rate in the treatment group is equal to that of the control group. In addition, two-sided 95% confidence intervals for the difference in response rate between arms will be calculated using a normal distribution approximation. The null hypothesis will be rejected at the two-sided 0.05 significance level. Subjects who were deemed a Treatment Success for the efficacy analysis and exited prior to their 6 month follow-up will be conservatively counted as a sustained treatment failure for the purpose of this analysis.

An analysis of time to CDI occurrence after completion of the assigned blinded treatment will be analyzed and presented by the Kaplan-Meier procedure and median duration presented by days (and weeks) using the ITT, mITT, and PP populations. The estimates will be presented for each of the time points at which CDI recurrence assessments are scheduled to occur. A graphic presentation of the Kaplan-Meier estimates will supplement the tabular presentation. Between group comparisons will be performed using the log-rank test.

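### The ITT run counts treated early exits as failures in both arms, so it is not guaranteed conservative, and no planned analysis bounds the effect of missing week-8 outcomes.

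*SAP*

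**What the plan says.** SAP 7.6.1.2 gives the reason for the label: "The ITT analysis will serve as the conservative analysis as it considers all subjects who exit prior to the 8-week efficacy assessment" as treatment failures. SAP 6.3.1 supplies the rule: "Randomized and treated subjects who exited prior to their 8-week efficacy assessment will be counted as treatment failures". It is not limited to one arm and does not depend on the reason for exit. Subjects who leave before treatment are dropped from the ITT analysis, and attempted but undelivered enemas count as failures.

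The other planned analyses handle early exits as follows.

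- **mITT (SAP 6.3.2, primary):** removes "subjects who discontinue from the study prior to evaluation of treatment failure/success for the primary endpoint" when the reason is unrelated to CDI symptoms; withdrawal of consent is a listed example. CDI-related exits are failures here too.
- **PP (SAP 6.3.3):** treats exits as the mITT does.
- **Time to recurrence (SAP 7.6.1.2):** the Kaplan-Meier and Cox analyses censor discontinuations at the last assessment up to week 8.
- **General rule (SAP 8.3):** no imputation, apart from carrying forward the Cdiff32 scores.

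The remaining sensitivity analyses vary the borrowing, the 2014-01 population and the covariates. SAP 7.6.2.1 uses similar language for the 6-month endpoint: a week-8 success who exits later "will be conservatively counted as a sustained treatment failure for the purpose of this analysis", again in both arms.

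**The concern.** A conservative check on a superiority claim should make the claim harder to sustain. Counting exits as failures lowers both arms' success rates. If enough placebo subjects leave, the placebo rate falls further and the difference grows. Agreement between the ITT and the mITT could then be read as robustness when the imputation rule helped to produce it.

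The missing-data question also has two sides. RBX2660 exits who in fact recurred threaten the claim, and the ITT covers that side. Placebo exits who in fact stayed free of CDI threaten it as well, and no planned analysis covers that. A possible route to unequal exit is visible in SAP 4.2, which tells subjects to disregard product features "such as the presence or absence of color or odor".

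**Working it through.** **Inputs.** SAP 4.4: "To demonstrate a 69% success with one dose of the RBX2660 treatment group", against "47% success in the Placebo control group, 240 subjects are required (power > 90%, nominal 2.5% type I error rate"). Hence pR = 0.69 and pP = 0.47. Allocation is 2:1, about 180 and 90. For attrition: "Up to an additional 30 subjects will be enrolled to allow for a 10% loss-to-follow up rate". No exit rate by arm is given, so every split below is an assumption.

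**The plan's own figure.** The normal-approximation power for 160 against 80 at 69% and 47%, one-sided 2.5%, is 0.910, which agrees with the stated power above 90% at 240. Then 240/0.90 = 267, close to the planned 270.

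**Formulas.** Let dR and dP be the rates of treated non-CDI exits before week 8, with exits unrelated to outcome.

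- mITT difference = pR − pP = 0.220.
- ITT difference = pR(1 − dR) − pP(1 − dP).
- The ITT exceeds the mITT when dP·pP > dR·pR, that is when dP/dR > pR/pP = 0.69/0.47 = 1.47. With no effect, pR = pP and the threshold is 1.
- Extreme bound (RBX2660 exits fail, placebo exits succeed) = pR(1 − dR) − [pP(1 − dP) + dP] = ITT difference − dP.

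**Results at 69% and 47%, in percentage points (mITT is 22.0 throughout).**

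| Exits RBX2660 / placebo | Ratio | ITT | Extreme bound |
|---|---|---|---|
| 10% / 10% | 1.00 | 62.1 − 42.3 = 19.8 | 9.8 |
| 9% / 12% | 1.33 | 62.8 − 41.4 = 21.4 | 9.4 |
| 7.5% / 15% | 2.00 | 63.8 − 40.0 = 23.9 | 8.9 |
| 6.7% / 16.7% (12 and 15 subjects) | 2.50 | 64.4 − 39.2 = 25.2 | 8.6 |

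The 7.5%/15% row is 27 exits divided equally by number, 13.5 per arm on average; under 2:1 allocation this gives placebo twice the RBX2660 rate. Differences are taken before rounding.

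At balanced 10% exits, a Pearson chi-square on expected counts gives p = 0.002 for the ITT and p = 0.12 for the extreme bound.

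**No true effect (47% in both arms).** The ITT difference is 0.47 × (dP − dR). At 7.5%/15% that is 0.47 × 0.075 = 0.035. Exact binomial enumeration at 180/90, with a pooled z test on this trial's data alone and a single look, gives these one-sided ITT rejection rates:

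| Exits RBX2660 / placebo | Cutoff 1.960 | Cutoff 1.996 (normal quantile of 0.97706) |
|---|---|---|
| 10% / 10% | 2.5% | 2.3% |
| 7.5% / 15% | 7.9% | 7.4% |
| 6.7% / 16.7% | 11.0% | 10.4% |

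**Coverage.** Non-CDI exits are deleted (mITT, PP), failed (ITT) or censored (Kaplan-Meier, Cox). Each rule is the same in both arms. The dropout example in the SAP appendix also applies one 10% rate to both arms, so unequal exit is not examined there.

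**The case against.** The case for the plan is substantial, and it rules out several stronger readings that a reader might infer.

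- **That any excess of placebo exits inflates the ITT effect.** This holds only with no effect. At the planning rates the ratio must pass 1.47; at 9%/12% the ITT is still below the mITT.
- **That the trial's false-positive rate rises to 7% to 8%.** It does not. SAP 6.3 and 7.6.1.1 rest study success on the mITT, and SAP 6.3.1 makes the ITT a sensitivity analysis. When exits are unrelated to outcome, as assumed above, the mITT comparison is itself unbiased.
- **That placebo subjects will leave more often.** The documents do not show it. A documented failure in either arm may receive open-label RBX2660 by staying in the study (Protocol 3.8), which is a reason to stay. In 2014-01, moving from the primary-analysis set to the ITT set adds two non-responders to one-dose RBX2660 (25/42 to 25/44) and none to placebo (19/44). The difference falls from 0.163 to 0.136, against RBX2660. The reasons for both additions are not fully stated, and one earlier study does not settle this one, but it lends the fear no support.
- **That placebo exits being successes is the only threatening direction.** RBX2660 exits who recurred matter too, and the ITT addresses them.

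Two further points stand. CDI-related exits already fail in the mITT, so only treated non-CDI exits and incomplete enemas separate the two analyses; treating the whole 10% as non-CDI is an upper case. And SAP 7.1 already plans discontinuations by group and reason, from which a reader could work out a worst case. The extreme corner is harsh: it loses significance at balanced 10% exits even with the full design effect, so it should not be a pass/fail test.

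None of this makes the label correct or supplies the missing bound.

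**Conclusion.** The point holds in a limited form. The ITT run is not conservative by construction. It shrinks the effect under equal or modestly unequal exits and enlarges it when the placebo rate of non-CDI exits exceeds about 1.47 times the RBX2660 rate at 69% and 47%, or by any placebo excess when there is no effect. The inflation is modest in the main example, about 2 points at 7.5%/15%.

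The firmer finding is the absence of a bound, which does not depend on unequal exits: at balanced 10% exits the ITT shows 19.8 points while the extreme bound is 9.8.

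These sizes assume that 10% of 270 treated subjects exit before week 8, that all those exits are non-CDI, and the stated splits by arm. The rejection rates also assume no borrowing and a single final look. The primary analysis and its error control are not in question here.

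**What to change.** 1. In SAP 7.6.1.2, replace the conservative label with *exit = failure analysis*.
2. Add a two-way tipping-point grid for treated non-CDI exits before week 8. Vary their success probability from 0 to 100% separately by arm, and report where the posterior probability, with and without borrowing, crosses the success thresholds (0.97706, and 0.99943 or its updated final value).
3. Show the corner in which RBX2660 exits fail and placebo exits succeed as the extreme bound, not as the pass/fail test.
4. Read the grid beside the by-arm discontinuation table already planned in SAP 7.1.
5. In SAP 7.6.2.1, drop the word conservatively, since the same both-arms rule applies to exits after week 8.

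The cost is a few words and one short program on data already collected; the primary analysis is unchanged. The downside is that the bound will look less favourable than the present ITT run.

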An analysis of time to CDI recurrence after completion of the assigned blinded treatment will be analyzed and presented by the Kaplan-Meier procedure and median duration presented by days (and weeks) using the ITT, mITT, and PP populations. The Kaplan-Meier estimate of the median time (days) and the associated 95% confidence interval will be presented for each treatment group. A graphic presentation of the Kaplan-Meier estimates will supplement the tabular presentation. Between group comparisons will be performed using the stratified log-rank test based on the stratification factor at randomization. The corresponding hazard ratio of the treatment effect along with the 95% confidence interval will be calculated using a Cox proportional hazard model with treatment and the stratification factor at randomization as explanatory variables.

Time to CDI recurrence is defined as the number of days from enema administration to first assessment indicating recurrence for those subjects who were deemed Treatment Failures with CDI recurrence. All subjects who are Indeterminate or discontinued for any reason prior to assessment of efficacy will be censored at the last assessment date at/prior to Week 8. For the analysis of Time to CDI recurrence within 8 weeks, all subjects considered as a treatment success will be censored at the date of their 8-week assessment. For the analysis of Time to CDI

recurrence through 6 months, all subjects considered to have achieved sustained clinical response will be censored at the date of their 6-month assessment.

Finally, the sensitivity of the primary efficacy endpoint will be assessed in a multivariate logistic regression adjusting for possible interactions of the following covariates with treatment group: age (< 65 years, \geq 65 years), sex (Female, Male), race group (White, Non-white), ethnicity (Hispanic-Latino, not Hispanic-Latino), site geography (outside the US, Eastern US*, Southern US*, Northern US*, Western US*), randomization strata (i.e., treatment received at the qualifying event) and number of previous episodes of CDI recurrence at baseline. Other baseline variables will be compared for balance using the appropriate statistical test. This analysis will be performed on all analysis populations where at least 20 subjects in each sub-group are available for analysis to fully understand the observed treatment effect.

*States included in the identified US geographical regions are as follows:

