Time to CDI occurrence is defined as the number of days from enema administration to first assessment indicating recurrence, for those subjects who were deemed Treatment Failures or Indeterminate. Randomized subjects who do not complete the assigned blinded treatment will be censored at Day 0. All subjects who are discontinued for any reason prior to the 6-month timepoint will be censored at the last assessment date at/prior to Month 6. All subjects considered as a sustained treatment success will be censored at the date of their 6-month assessment.

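### The 8-week time-to-recurrence analysis can censor CDI-related exits that the primary analysis counts as failures, and the SAP gives Indeterminate subjects two opposite rules

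*SAP*

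**What the plan says.** - **Event rule (SAP 7.6.1.2).** Time to recurrence runs from the enema to the first assessment that indicates recurrence, "for those subjects who were deemed Treatment Failures with CDI recurrence".
- **Censoring rule (same section).** "All subjects who are Indeterminate or discontinued for any reason prior to assessment of efficacy will be censored at the last assessment date" at or before week 8.
- **Populations (same section).** The analysis is presented with "median duration presented by days (and weeks) using the ITT, mITT, and PP populations". No censoring rule is specific to a population.
- **mITT (SAP 6.3.2).** The set leaves out "subjects who discontinue from the study prior to evaluation of treatment failure/success for the primary endpoint if the reason for exit is not related" (that is, where CDI symptoms were not the cause). For the others, "Subjects who were exited prior to the 8-week efficacy assessment due to CDI related symptoms will be counted as treatment failures", even when the required documentation is missing.
- **PP (SAP 6.3.3).** Exits not related to CDI are excluded in the same way as in mITT.
- **ITT (SAP 6.3.1).** "Randomized and treated subjects who exited prior to their 8-week efficacy assessment will be counted as treatment failures". This covers treated subjects only; for those who left beforehand, exits prior "to receiving blinded treatment will not be included in the analysis".
- **6-month time to CDI occurrence (SAP 7.6.2.1).** The event time is defined "for those subjects who were deemed Treatment Failures or Indeterminate".
- **Overlap.** SAP 7.6.1.2 also sets a censoring rule for time to recurrence through 6 months, so both sections govern the 6-month curve.

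**The concern.** A supportive time-to-event analysis should normally use the same events as the primary endpoint and add only their timing. Here a subject who leaves because of CDI symptoms, without a confirmed recurrence, is a failure in the primary proportion but may be censored in the curve. The subject leaves because the event is probably happening, so the censoring is not independent of the outcome.

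The plan foresees such subjects. SAP 6.3.2 provides for CDI-related exits that lack failure documentation, and SAP 4.1 exits subjects who have an on-study CDI episode and will be treated outside the protocol.

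Two things are at stake. The Kaplan-Meier estimates and hazard ratio could differ from the primary proportions purely because of coding. Also, two programmers following the same text could produce different results, both for these exits and for Indeterminate subjects.

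**Working it through.** **1. Which early exits can the censoring rule reach?**

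| Subject | Binary rule | SAP 7.6.1.2 time-to-recurrence |
|---|---|---|
| Failure with recurrence established before exit | Failure | Event (no conflict) |
| CDI-related exit before efficacy assessment, mITT | Failure, documented or not | Censored under the discontinuation clause; an event only if read as a failure with recurrence |
| The same, PP | Retained; follows mITT by cross-reference | As above |
| Non-CDI exit, mITT or PP | Excluded from the set | Not present |
| Any treated exit before week 8, ITT | Failure | Censored |
| Indeterminate | No rule stated | Censored here; event in SAP 7.6.2.1 |

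In mITT and PP the phrase about discontinuing for any reason therefore has only CDI-related exits left to act on.

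**2. The plan's own figures.** Inputs from SAP 4.3 and 4.4: success 69% and 47%, 2:1 allocation, power above 90%, nominal 2.5% type I error (taken as one-sided).

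- Placebo n = [1.96·√(p̄q̄·1.5) + 1.2816·√(0.47·0.53 + 0.69·0.31/2)]² / 0.22², with p̄ = (0.47 + 2·0.69)/3 = 0.617. This gives 77.1, rounded up to 78, so the total is 78 + 156 = 234, against 240 stated. Power at 80 and 160 is 91.0%.
- SAP 6.4.2 states 99.5% log-rank power at 6 months with 104 per group. Under its exponential model the hazard ratio is ln 0.69 / ln 0.47 = 0.491. With 26/8 = 3.25 eight-week periods, events = 104(1 − 0.69^3.25) + 104(1 − 0.47^3.25) ≈ 168. Schoenfeld power is 99.6%; 5,000 simulated trials also give 99.6%.

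Both figures reproduce, so 69%, 47% and 0.491 are a fair base.

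**3. Effect of censoring some failures.** Let f be the fraction of an arm's failures that exit unconfirmed and are censored. The documents give no value, so f is an assumption. The hazard that remains is (1 − f) times the true one, so:

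- Kaplan-Meier success = p^(1 − f)
- hazard ratio = 0.491 × (1 − f_RBX)/(1 − f_placebo)

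Power is for an unstratified two-sided 0.05 log-rank test with 180 and 90 subjects (4,000 simulated trials per case).

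| f RBX2660 | f placebo | Success RBX2660 | Success placebo | Difference (points) | Hazard ratio | Power |
|---|---|---|---|---|---|---|
| 0 | 0 | 69.0% | 47.0% | 22.0 | 0.491 | about 95% |
| 10% | 10% | 71.6% | 50.7% | 20.9 | 0.491 | about 92% |
| 20% | 20% | 74.3% | 54.7% | 19.7 | 0.491 | about 89% |
| 10% | 20% | 71.6% | 54.7% | 16.9 | 0.553 | about 79% |
| 20% | 10% | 74.3% | 50.7% | 23.6 | 0.437 | about 97% |

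**4. Does one arm lose more?** With f = 10% in both arms, the per-subject loss is 0.53 × 0.10 = 5.3% on placebo and 0.31 × 0.10 = 3.1% on RBX2660. In counts it is 90 × 0.053 = 4.8 and 180 × 0.031 = 5.6, so fewer on placebo.

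**5. ITT.** Suppose 10% of each arm exits for reasons unrelated to outcome. Counting them as failures gives 0.69 × 0.9 = 62.1% and 0.47 × 0.9 = 42.3%, a difference of 19.8 points. Censoring them returns about 69% and 47%.

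**The case against.** The best reply is that this is a supportive analysis with narrow exposure. Suspected recurrence requires a visit and a stool test (Protocol 6.13), and cases without a central result go to the adjudication committee (SAP 4.1.3). Most CDI-related exits may therefore already be adjudicated failures, and so events. That stands: the conflict concerns only exits without an established recurrence, plus Indeterminate outcomes. It does not remove the conflict, because SAP 6.3.2 explicitly counts undocumented CDI exits as failures and SAP 7.6.1.2 does not say how to code them.

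A reader might infer more in four ways, none of which the documents support.

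- **Failures are dropped more often on placebo.** No exit rates by arm are given. Equal fractional loss leaves the hazard ratio unchanged, and 2:1 allocation can put the larger count on RBX2660.
- **The rule favours RBX2660.** It does so only if a larger share of RBX2660 failures is censored. Extra placebo loss works against RBX2660.
- **Early exits go unchecked.** The same section repeats the primary analysis in ITT with treated exits as failures, and adds chi-square and no-borrowing versions. SAP 7.6.1.2 attaches the conservative role to that binary repeat, not to the ITT curve.
- **Every ITT exit must be a recurrence event.** Counting unrelated withdrawals or deaths as recurrences makes a different composite endpoint. Censoring them is a common convention.

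**Conclusion.** The concern holds in a limited form. In mITT and PP the discontinuation clause of SAP 7.6.1.2 acts only on CDI-related exits, which the primary analysis treats as failures, and the section leaves the choice between event and censoring open. The Indeterminate conflict between SAP 7.6.1.2 and 7.6.2.1 is separate and clear from the text; neither section defines the term.

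The size cannot be fixed from the documents. With 10% to 20% of failures lost per arm, the week-8 difference runs from 16.9 to 23.6 points and the hazard ratio from 0.437 to 0.553, against 22.0 and 0.491. These figures assume the planned rates, proportional hazards, and losses spread evenly over the failures within each arm. A reader should not infer that the primary result is at risk: the Bayesian mITT decision and its binary ITT repeat do not use this censoring rule.

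**What to change.** In SAP 7.6.1.2:

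- For mITT and PP, count exits before week 8 due to CDI symptoms as events at the exit date (or the first symptom date, chosen in advance), matching SAP 6.3.2. State that this overrides the discontinuation clause.
- Keep the present censoring rule as a labelled supplementary analysis.
- For ITT, count at least the CDI-related exits as events. A version with all treated exits as events, to match SAP 6.3.1, is optional and should be labelled as a sensitivity analysis. If it is run, also state how unsuccessful enema delivery is coded, since SAP 6.3.1 counts it as failure.

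In SAP 7.6.1.2 and 7.6.2.1, define Indeterminate once and apply one rule in both. Write the same rule into the binary primary analysis.

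The cost is SAP wording and programming before unblinding. No new data are needed, because SAP 6.3.2 already captures the reason for exit on the exit form.
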